Official title: Mindfulness-Based Intervention for Caregivers of Frail older adults:
Towards a model of intergenerational caregiving for Chinese families

NCT number: to be assigned

Document date: April 22, 2021

The research questions of the proposed study are:

- 1) investigate the effects of a brief mindfulness-based intervention for caregivers of frail elders in reducing caregiver burden and depression;
- 2) compare the effects of mindfulness-based intervention with an evidence-based caregiver programme; and
- 3) explore the factors that contribute to the positive improvements of both caregiver programmes, and develop a preliminary model for understanding and reducing caregiver burden and depression.

RESEARCH PLAN AND METHODOLOGY

Study design

In view of the research objectives about efficacy of the MBI and in the interest of developing a model of mediators in the MBI and intergenerational caregiving, a multi-site, three-arm, randomized controlled trial will be implemented (Baron et al., 2013). The effects of the MBI for caregivers for frail elderly will be tested by comparing the MBI (Arm 1), with psychoeducation (Arm 2), and treatment-as-usual (Arm 3). Assessments will be scheduled pre-intervention (T0), post-intervention (T1), and at 6-month follow-up (T2). The program effects will be tested using both pairwise between-subject comparisons (Arm 1 vs Arm 2, Arm 2 vs Arm 3, and Arm 1 vs Arm 3) and within-subject comparisons (measures at T0, T1, and T2). The between-group analyses will be adjusted for baseline scores and for factors related to outcomes, including the age and sex of the caregivers, the severity of depression, anxiety, caregiver burden, and the level of frailty of elderly. Refinement of design from a pilot study. A pilot study has been conducted in August to September 2019.

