Sample size estimation. We calculated the sample size needed for the first two hypotheses and choose the larger one for the estimation of overall sample size. For the first hypothesis, the calculation is based on a previous study of an MBI for caregivers (Hou et al., 2014), in which an effect size of 0.64 in depression, with an estimation of an effect size of 0.14 for Arm 3. For a two-tailed α error of 5%, an 80% power, and a test of three independent groups, the required sample size will be 64 per arm (Cohen, 1988). For the second hypothesis, the calculation is based on a non-inferiority comparison was conducted. A non-inferiority margin of 50%, as common practice in non-inferiority trials (Althunian et al., 2017), is selected and the required sample size will be 51 per arm. We further adjust the sample size based on an estimation of drop-out rate and intra-class correlation. An estimation of a drop-out rate of 15% is based on two local studies of mindfulness-based intervention (Hou et al., 2014; Lo et al.,

2015). Besides, an estimation of intra-class correlations of 0.07 is based on PI's two recent mindfulness multi-site studies ranged from 0 to 0.07 (Lo et al., 2017; Lo et al., in press), and 240 caregivers will be recruited for this study. Based on such estimation, it should also be necessary to conduct mediational studies with .8 statistical power (Fritz & MacKinnon, 2007).

Recruitment of participants. The inclusion criteria for participation in this study are: 1) Caregivers of frail elderly based on a professional's assessment of Clinical Frailty Scale with a score of 6, indicating a moderate level of frailty or above (Rockwood et al., 2005). 2) Caregivers being adult children or children in-law of the elder care receiver. 3) Caregivers who are experiencing caregiver burden at the time of study, with scores of 8 or above in ZBI-4 (Bedard et al., 2001). The exclusion criteria include: 1) Caregivers who have diagnoses of psychosis, developmental disabilities, or cognitive impairment, which may present difficulties in comprehending the content of the program. 2) Spouses, siblings, or friends will be excluded as their burden or depressive symptoms may be attributed to different reasons. 3) Caregivers of elders with moderate to severe dementia will be excluded and the Clinical Dementia Rating Scale will be administered (Huges et al., 1982), and 4) Caregivers who had participated in a MBSR or equivalent.

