Caregiver burden - Measured by 22-item Zarit Burden Interview (ZBI) (Zarit et al., 1980)	$\alpha = .88$ (Tang et al., 2017)
Secondary outcome variables	
Depressive symptoms - measured by 10-item The Center for Epidemiologic Studies Depression Scale (CES-D) (Radloff, 1977)	$\alpha = 0.78$ (Boey, 1999)
Anxiety symptoms - measured by 7-item Hospital Anxiety and Depression Scale – Anxiety subscale (HAD-A) (Zigmond & Snaith, 1983)	$\alpha = 0.77$ to 0.82 (Leung et al., 1999)
Positive caregiving experiences - Measured by 9-item Positive Aspects of Caregiving Scale (PAC) (Tarlow et al., 2004)	$\alpha = 0.89$ (Lou et al., 2015)
Spiritual well-being - measured by 12-item Functional Assessment of Chronic Illness Therapy–Spiritual Well-Being Scale (FACIT-Sp-12) (Peterman et al., 2002), with two subscales in meaning/peace and faith	$\alpha = 0.80$ (Wang, 2016)
Family conflicts - measured by 10-item Revised Conflict Tactics Scale (CTS2) (Beach et al., 2005), with subscales in psychological mistreatment (5 items) and physical abuse (5-items)	$\alpha = .81$ to $.82$ (Yan & Tang, 2001)
Biomarker: Heart rate variability - measured by the CorSense Heart Rate Variability monitor	N.A.
Mediators of outcome	
Cognitive factor: Coping styles - measured by 28-item brief COPE (Carver, 1997), with 11 subscales (problem-solving, accommodation, support-seeking, behavioral disengagement, denial, self-distraction, self-blame, humour, venting, substance use, and religion)	$\alpha = 0.76$ for whole scale, and $\alpha = .49$ to $.87$ for subscales (Tang et al., 2016)
Cognitive factor (psychoeducation-specific): Self efficacy - Measured by 5-item subscale of controlling upsetting thoughts (5 items) in the Revised Scale for Caregiving Self-Efficacy (RSCSE) (Steffen et al., 2002)	$\alpha = .86$ (Au et al., 2009)
Cognitive factor (mindfulness-specific): Experiential avoidance - measured by 15-item The Brief Experiential Avoidance (BEAQ) Questionnaire (Gamez et al., 2011)	$\alpha = 0.81$ (Lo et al., in review)

3. Data Analyses

[figure not shown]

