All analyses will be carried out according to the intention-to-treat approach and all participants who receive randomization and allocation to one of three treatment arms will be included for analyses (Moher et al., 2010). Repeated measure ANOVA will be used to evaluate the effects of the MBI (Arm 1), relative to PSY (Arm 2) and TAU (Arm 3), and the analyses of the primary and secondary outcome measures will be analyzed. In addition to the immediate programme effects, outcomes measured at T1 and T2 will be compared, to assess whether maintenance effects will be sustained at 6-months.

The mediation effects on the relationships between group (MBI or PSY vs. TAU)

variables and caregiver outcome variables (ZBI, CES-D, HAD-A), controlling the baseline variables (sex and age of caregivers, frailty score), will be evaluated using the PROCESS macro in SPSS (Hayes, 2012), in order to compute the effect of the independent variable on the mediator (a), the effect of the mediator on the dependent variable (b), total effect (c), direct effect (c'), and bootstrapped (i.e., 10,000 random samples) bias-corrected 95% confidence intervals of the indirect effect (ab).

According to Hayes (2009), with significant paths a and b, even without a significant path c, confidence intervals that do not include zero indicate a significant indirect (i.e., mediation) effect.

Appendix 1
Recruitment Flowchart

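### Repeated-measures ANOVA in its standard form would analyse about 204 of 240 caregivers, not all randomised, and within-arm T1–T2 change cannot separate maintained benefit from the end of caregiving

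*Combined protocol and SAP*

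**What the plan says.** Recruitment of participants sets a minimum frailty for the elder, "with a score of 6, indicating a moderate level of frailty or above", with no upper limit. It also requires current burden in the caregiver: "Caregivers who are experiencing caregiver burden at the time of study, with scores of 8 or above in ZBI-4". It does not require the elder to live at home.

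Study design schedules assessments at T0, T1 and a six-month T2. Table 1 names the 22-item ZBI as the only primary outcome.

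Data Analyses states the intention-to-treat principle: "all participants who receive randomization and allocation to one of three treatment arms will be included for analyses". It names repeated-measures ANOVA as the method for comparing MBI with psychoeducation and usual care. On durability it says that "outcomes measured at T1 and T2 will be compared, to assess whether maintenance effects will be sustained at 6-months".

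Study design adds pairwise between-arm comparisons adjusted for baseline. The adjustment factors are caregiver age and sex and the severity of depression, anxiety, "caregiver burden, and the level of frailty of elderly". Sample size estimation allows for 15% drop-out, taken from earlier mindfulness studies.

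No section gives a method for missing data. None mentions the elder's death, placement or the end of caregiving, or says how the ZBI is collected or used afterwards.

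**The concern.** There are two linked problems.

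**Missing T2.** Standard repeated-measures ANOVA needs a value at every time point. A caregiver who completes T0 and T1 but misses T2 is removed altogether. The plan promises an analysis of everyone randomised and also expects drop-out, so the named method in its usual form does not deliver the promise. The loss need not be random. In this population one plausible reason for missing T2 is that the elder has died, so a complete-case analysis can favour caregivers whose caring role continued.

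**Reading maintenance from T1 to T2.** Everyone enters with burden from caring for a frail elder. If that role ends before T2, ZBI may fall with no contribution from the programme. Within one arm, such a fall looks the same as a benefit that was kept or grew. Baseline frailty as a covariate cannot account for an event that happens later.

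The six-month conclusion on the primary outcome is at stake, together with T1 data that have already been collected.

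**Working it through.** **1. The plan's own figure.** Inputs from Sample size estimation: effect sizes 0.64 and 0.14 (difference 0.50 SD), two-sided 5%, 80% power. Normal approximation: n = 2 × (1.960 + 0.842)² / 0.50² = 62.8, so 63. The t-based solution is 63.8, so 64 per arm, as stated. The total of 240 is close to 3 × 64 × 1.07 / 0.85 = 241.7. No allowance for the end of caregiving beyond the 15% is stated.

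**2. How many a complete-case ANOVA keeps.** 240 × 0.85 = 204, so 36 caregivers are dropped. With equal allocation (the ratio is not stated) this is 80 × 0.85 = 68 per arm. The documents do not split drop-out between T1 and T2. If all of it fell after T1, 36 caregivers with usable T1 data would be discarded. For a T1 contrast of 0.50 SD, noncentral-t power is about 88% with 80 per arm and 82.5% with 68 (83.0% by normal approximation), ignoring clustering. That is the upper bound of the loss at T1; it is smaller if some leave before T1.

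**3. End of caregiving, with ZBI still collected.** The documents give neither an event rate nor a change in ZBI. Assumptions: a proportion p of 2–15% by T2, equal in all arms; a ZBI fall of k = 1 SD afterwards; no programme effect in those caregivers; 0.50 SD in the rest; 68 per arm; clustering ignored.

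- Within-arm shift = p × k
- Between-arm difference = 0.50 × (1 − p)
- SD (approximate) = √(1 + p(1 − p)k²)
- Standardised effect d = difference / SD

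| p | Within-arm shift (SD) | Difference | SD | d | Power at T2 |
|---|---|---|---|---|---|
| 0 | 0 | 0.500 | 1.000 | 0.500 | 82.5% |
| 2% | 0.02 | 0.490 | 1.010 | 0.485 | 80% |
| 5% | 0.05 | 0.475 | 1.023 | 0.464 | 77% |
| 10% | 0.10 | 0.450 | 1.044 | 0.431 | 70% |
| 15% | 0.15 | 0.425 | 1.062 | 0.400 | 64% |

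Powers are noncentral t, two-sided 5%.

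**4. Unequal events.** If the event proportion differs by 5 percentage points between two arms, the contrast is biased by 0.05 × 1 = 0.05 SD.

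**5. Is there a control at T2?** Study design lists T2 without restricting it to particular arms, and Recruitment of participants withholds both programmes from Arm 3 until after T2. Implementation and assessment, however, describes T2 as a booster and final assessment for Arms 1 and 2. If Arm 3 is not assessed at T2, there is no usual-care arm against which to judge the drift in step 3.

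**The case against.** **The plan is silent on missing data, not contradictory.** This is fair. Complete-case deletion is the standard behaviour of the named method, not something the plan states. The baseline-adjusted pairwise comparisons in Study design could be run at T1 without T2 data. But the plan does not say how they relate to the ANOVA, and nothing it names ensures that all randomised caregivers are analysed.

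**The randomised contrast protects against drift.** A reader might infer that the end of caregiving would be counted as programme benefit throughout. The documents do not support that. A fall common to all arms cancels in the between-arm comparison and only dilutes it, which is conservative for superiority. The false reading arises in the within-arm T1–T2 comparison, or if events differ by arm.

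**The size is unknown.** This stands. A reader could pair 15% events with a 1.5 SD fall and 64 per arm and obtain 56% power. That joins the worst values of two unsourced assumptions to a sample smaller than the 68 per arm that the plan's own drop-out leaves. In addition, the 0.50 SD comes from depression and not ZBI, the plan names no time point for its power, and few events would be expected by T1, after only four bi-weekly sessions.

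**Placement is not the end of caregiving.** This also stands. Eligibility does not require the elder to live at home, so placement as such is no ground for setting ZBI aside. Nor is the direction fixed for every outcome: bereavement could worsen depression or anxiety scores.

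**Conclusion.** The concern holds in two limited parts.

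First, the stated analysis set and the named method do not fit together. On the plan's own 15% drop-out, the standard ANOVA uses about 204 of 240 caregivers. This needs no outside figure, only the usual form of the method.

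Second, T1-to-T2 change within an arm cannot by itself show maintenance, because the end of caregiving can lower ZBI with no programme effect. Under the assumptions above, the shift is 0.02–0.15 SD and power at T2 falls from 82.5% to between 80% and 64%. With rare events the effect is small. These figures show sensitivity and do not estimate what will happen in this trial.

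The documents do not support concluding that the between-arm result is biased towards benefit, unless events differ by arm, or that ZBI loses its meaning once an elder enters residential care.

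**What to change.** In Data Analyses:

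1. Replace the repeated-measures ANOVA with a mixed model for repeated measures using all available T0–T2 data: arm, time, arm-by-time, baseline ZBI and the covariates already named. If T1 and T2 are the responses, T0 enters once, as the baseline covariate. State the missing-at-random assumption, and report by arm those with no post-baseline value, since they add nothing to the contrast.
2. Judge maintenance by the between-arm contrast at T2, with within-arm T1–T2 change as description only. Reconcile Study design with Implementation and assessment on whether Arm 3 is assessed at T2.
3. At T1 and T2, record whether the elder has died or caregiving has ended, and when. Report this by arm beside the T2 result.
4. Keep all observed outcomes in the main analysis. Add a sensitivity analysis that leaves out ZBI collected after caregiving ended, not after placement as such. Because it conditions on an event after randomisation, it should support the main result and not replace it.

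The cost is one extra question at two visits and slightly more analysis. Sample size, eligibility and the programmes are unchanged.

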The research project will be announced and promoted among collaborating NGOs and through advertisement in social media, promotional emails, and project leaflets. Four NGOs have indicated their intentions to contribute to this study by assisting in promotion, recruitment, program implementation and data collection. Support letters of these NGO collaborators have been provided in the appendix.

We will organize briefing sessions for explaining the rationale and procedures of the study half yearly. All interested caregivers will be screened using Clinical Frailty Scale, Clinical Dementia Rating Scale, and caregiver stress. Written consent will be collected for eligible participants. All NGO collaborators will provide standard care to the participants, including participants in Arm 3 who will not receive MBI nor psychoeducation before T2. The Research Assistant who is blinded to the personal data of the participants, will administer the random assignment using computer generated programming. Participants will be randomly assigned to MBI (Arm 1), psychoeducation (Arm 2), or treatment-as-usual (Arm 3). During the recruitment and implementation, both arm 1 and 2 are called "Family Psychoeducation Program", and the term "mindfulness" will not be used for Arm 1 to minimize the potential placebo effect. Cash remuneration coupons will be provided to caregivers who can complete the study at T1 and T2. A recruitment flowchart is attached in Appendix 1.

Procedures

Program planning and training. The themes and content of arms 1 and 2 are summarized in Appendix 2.

MBI (Arm 1). Based on the protocols of PI's previous clinical trials, brief mindfulness exercises will be integrated with psychoeducation of caregiving for frail elderly. The protocol for Arm 1 has been developed on mid-Sept, 2019 for the first pilot study.

Psychoeducation.

(Arm 2). The research team will modify START (STrAtegies for RelaTives) program for

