caregivers of dementia (Livingstone et al., 2014) into a 10-hour group program. Major changes include the content originally related to the caregiving needs of dementia will changed to frail elderly. Two hours will be added to allow for more discussion of individual caregiver's concerns. The protocol for Arm 2 will be developed and a pilot study will be conducted shortly in early 2020. Arm 1 and 2 are parallel in program design. Both will be 4-session programs to be organized bi-weekly, and last for 10 hours in total. Both programs include 15-minute daily home practice assignments, with Arm 1 being guided with mindfulness exercises, and Arm 2 with coping and problem-solving skills. Both arms will be delivered in group format, with 10 to 15 caregivers in each group. Programs will be conducted in the service units of four NGO collaborators and PI's university. All instructors for Arm 1 require basic professional training in MBI, plus at least two-year experience in conducting MBI. Instructors for Arm 2 will be recruited from NGO with experience in working with caregivers of frail elderly for more than two years. Implementation and assessment.

After the pre-intervention assessment (T0), caregivers who meet inclusion criteria will be randomized into a MBI (Arm 1), psychoeducation (PSY, Arm 2), or treatment-as-usual (TAU, Arm 3). After the intervention programs, participants in three arms will complete the post-intervention assessment (T1). A 6-month follow up (T2) is offered as a booster and final assessment for arms 1 and 2. This study will be single-blinded and outcome assessors will be blinded to randomization status.

To ensure intervention fidelity, all program sessions will be audio-recorded and an independent rater will listen to 20% of the selected clips on random basis, and assess whether each element in the intervention protocol has been implemented with consistency. Higher concordance rates will signify greater fidelity to the intervention protocol, which will be carefully monitored throughout the study. The treatment fidelity of Arm 1 will be further assessed by Mindfulness-based Interventions-Teaching Assessment Criteria Scale (Crane et al., 2013). Those of Arm 2 will be assessed by a checklist for implementing START program.

Table 1. Outcome variables and measures

Study variables and measures	Validation in HK samples
Primary outcome variables	

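### The randomisation method is not specified beyond computer-generated assignment; allocating each closed site-cohort in equal thirds, with site in the model, would protect group size and within-site balance

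*Combined protocol and SAP*

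**What the plan says.** Under Recruitment of participants, the research assistant "will administer the random assignment using computer generated programming". That is the only description of the allocation method in the text. The ratio is not stated; 1:1:1 is implied by sample sizes given per arm.

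The unit is the individual and the timing is after baseline: "After the pre-intervention assessment (T0), caregivers who meet inclusion criteria will be randomized" (Implementation and assessment).

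On delivery, the Procedures section states: "Both arms will be delivered in group format, with 10 to 15 caregivers in each group". On location: "Programs will be conducted in the service units of four NGO collaborators", with the university as a fifth site. On recruitment waves: "We will organize briefing sessions for explaining the rationale and procedures of the study half yearly". The documents do not give cohort sizes, the number of groups per site, or whether caregivers from different sites may share a group.

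Study design calls the trial multi-site. It lists the adjustment factors as baseline scores, caregiver age and sex, severity of depression, anxiety and burden, and the elder's frailty. Site is in neither that list nor Data Analyses. Sample size estimation nevertheless allows for an intra-class correlation of 0.07, the top of a range of 0 to 0.07 seen in two earlier multi-site studies.

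**The concern.** Group size is part of how both programmes are defined, and it depends on how many caregivers at one place and time fall into each arm. With five sites and 240 caregivers there are about 48 per site if sites are equal, or 16 per arm. Each site would then run only one or two groups per programme arm, so chance variation in the split has little room to average out.

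If the split is left to unrestricted chance, a site may have to run a group outside 10 to 15, hold allocated caregivers for a later wave, or combine sites. The NGOs also provide standard care and supply the Arm 2 instructors, so sites may differ in ways that bear on outcome. With neither stratification nor a site term stated, nothing in the written plan removes those differences from the arm comparisons.

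**Working it through.** **Inputs from the documents.** Three arms; N = 240; five sites; groups of 10 to 15 in Arms 1 and 2; effect sizes 0.64 and 0.14; two-sided 5% alpha; 80% power; 15% drop-out; ICC 0.07.

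**Assumptions.** Simple 1:1:1 allocation; one group per programme arm in each site-cohort; equal sites (240 / 5 = 48).

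**The plan's own figure.** Difference 0.64 − 0.14 = 0.50 SD. n = 2 × (1.96 + 0.84)² / 0.50² ≈ 63 per arm; the t-test version is 63.8, rounded up to 64. The stated 64 is reproduced. The documents give no figure for group-size attainment or site balance.

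**Group size.** For a cohort of n, the counts in Arms 1 and 2 are trinomial with probabilities 1/3, 1/3, 1/3. Summing n! / (a! b! c!) × 3⁻ⁿ over a and b both from 10 to 15, with c = n − a − b:

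| Cohort size | Both groups in 10–15 |
|---|---|
| 30 | 24% |
| 33 | 42% |
| 36 | 52% |
| 37 (best case) | 53% |
| 40 | 46% |
| 42 | 38% |
| 45 | 23% |

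Letting an arm split into more than one group of 10 to 15 helps little at this scale (35% at 45).

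**If sites are pooled into a wave.** Under the same simple allocation, with as many groups as needed, both programme arms can be divided into groups of 10 to 15 in 84% of waves of 75, 92% of waves of 80 and more than 99% of waves of 100.

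**Balance within a site of 48.** The SD of one arm's count is √(48 × 1/3 × 2/3) = 3.3 around 16. The largest and smallest arms differ by 8 or more in 39% of draws. In simulation of five such sites, a ratio of 1.5:1 or worse occurs at 50% of sites, and at one or more sites in 97% of trials.

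**Power.** With exact balance and 85% retention there are 80 × 0.85 = 68 per arm. Then 0.50 × √(68/2) − 1.96 = 0.955, giving 83.0%. Simple allocation gives 82.7% on average, and 81.8% if the analysis is then stratified by site. These figures ignore clustering.

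**Precision from balancing and modelling site.** Take 0.07 as the share of variance between sites. With five sites, the expected spread around their own mean is 0.07 × 4/5 = 0.056. An unstratified, unadjusted contrast carries 0.93 + 0.056 = 0.986 of the variance; a balanced, site-adjusted one carries 0.93. The reduction is 0.056 / 0.986 = 5.7%, about 6%. At an ICC of 0 it is nil. This is separate from the power figures above, which contain no site variance.

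**What restricted allocation achieves.** Equal thirds of any closed cohort of 30 to 45, with arms differing by at most one, give 10 to 15 per arm. Running permuted blocks of 3 or 6 within a cohort is slightly weaker: no misses at the tested sizes from 32 to 43, about 4% at 31 or 44, and 13% to 14% at 30 or 45. A cohort of 48 gives 16 per arm and fails either way. Five cohorts of at most 45 reach only 225, so 240 needs at least six single-group cohorts; six of 40 work.

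**The case against.** The strongest reply is that the protocol is silent, not wrong. A reader might infer that the trial has no blocking. The documents do not say so: computer-generated assignment is compatible with permuted blocks, and the recruitment flowchart in Appendix 1, which might hold more detail, is not shown in the text available. This stands, and the finding is that the method is not specified.

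The miss rates also rest on a delivery model that the plan does not state. Briefings are for the study as a whole, recruitment includes social media and email, and nothing forbids grouping caregivers across sites. Under pooled waves of 75 or more the difficulty mostly disappears. This too stands.

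A reader might infer that blocking alone would secure the group size. It would not: equal sites of 48 still give 16 per arm after perfect blocking. Cohort size has to be set as well.

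A reader might also infer a waiting-time bias, with baseline going out of date in the programme arms only. The documents give no waiting times, and Implementation and assessment places T1 after the programmes for all three arms. Such a bias is possible but has not been shown. Nor does chance site imbalance bias a randomised comparison; it costs precision.

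What the reply leaves untouched is that a multi-site trial with a stated group size gives no restriction on allocation and no site term, while its own sample-size section expects clustering.

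**Conclusion.** The point holds in a conditional form. The allocation method is unspecified and site is missing from the listed covariates. If allocation is simple 1:1:1 and each site-cohort supplies one group per programme arm, the 10 to 15 target is met for both groups in only about 23% to 53% of cohorts of 30 to 45. A site of 48 shows an arm gap of 8 or more in 39% of draws.

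The loss of power from chance imbalance is about one point or less, so the sample size is not the reason to act. The reasons are orderly group delivery, balance within sites, and up to about 6% lower variance of an arm contrast. That last figure assumes that the plan's upper ICC of 0.07 describes a site effect. The change is worth making because it is cheap and because imbalance cannot be undone after allocation.

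**What to change.** State the sequence type and the 1:1:1 ratio, and replace the randomisation sentence with a rule to this effect:

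- Once a site-cohort of about 30 to 45 has completed T0 (for example, six cohorts of 40), it is closed and randomised in equal thirds from one concealed computer-generated list, stratified by site and cohort. A cohort of 40 splits 13, 13 and 14, with the arm receiving the extra place chosen at random.
- TAU members of a cohort have T1 and T2 in the same calendar weeks as that cohort's programme groups.
- Site is included in the between-arm model.

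If blocking by site is already built into the program, it need only be written down. If the intention is to pool sites into larger waves, the protocol should say so and give the wave size; site should still be a stratum and a model term.

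The cost is small but not nil. Allocation waits until a cohort is assembled, which group delivery largely requires anyway, and the model gains a few terms. N stays 240. Randomising a closed cohort in one step also avoids the predictability of small fixed blocks.

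### Arm 1 vs Arm 2 is sized as non-inferiority, but the plan gives only intention-to-treat analyses, with no non-inferiority test and no supporting per-protocol analysis

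*Combined protocol and SAP*

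**What the plan says.** Research question 2, on the opening page, is to "compare the effects of mindfulness-based intervention with an evidence-based caregiver programme". Under Sample size estimation the plan says: "For the second hypothesis, the calculation is based on a non-inferiority comparison was conducted". It continues: "A non-inferiority margin of 50%, as common practice in non-inferiority trials", and concludes that "the required sample size will be 51 per arm". It does not state the outcome, the scale of the margin, the effect of which 50% is taken, or the alpha and power for this hypothesis. That the second hypothesis means Arm 1 vs Arm 2 is inferred from research question 2.

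Section 3, Data Analyses, opens: "All analyses will be carried out according to the intention-to-treat approach". The analysis set is defined in the same sentence: "all participants who receive randomization and allocation to one of three treatment arms will be included for analyses". The method is repeated measures ANOVA. The section gives no confidence limit to be set against the margin, no per-protocol or attendance-based set, no attendance threshold, no sensitivity analysis and no method for missing data.

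**The concern.** In a superiority comparison, keeping non-attenders in the analysis usually works against a positive finding. In a non-inferiority comparison it can work in favour of one. Caregivers who attend neither programme receive little of either, so if similar shares of both arms stay away, a real difference between the programmes is diluted and the observed difference moves towards zero.

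The design makes this pattern plausible. Both programmes have four group sessions, one every two weeks, and daily home practice, so exposure depends on the caregiver. The fidelity procedures rate delivery of the programme, not how much of it each caregiver received. A finding that mindfulness is non-inferior to psychoeducation could therefore partly reflect attendance, and the planned Arm 1 vs Arm 2 output would not separate the two explanations.

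**Working it through.** **Inputs from the plan.** 51 per arm for the second hypothesis; a margin of 50%; effect sizes of 0.64 for mindfulness and 0.14 for Arm 3, a gap of 0.50; drop-out 15%; intra-class correlation 0.07; groups of 10 to 15; 240 caregivers in total.

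**Assumptions not in the plan.** Margin 0.50 SD; one-sided alpha 5%; 80% power (stated for the first hypothesis only); equal allocation, so 240 / 3 = 80 per arm; a share q of non-attenders in each arm, whose outcomes do not depend on arm.

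**Step 1: reproduce 51 per arm.** With no true difference, n = 2 × (1.645 + 0.842)² / 0.50² = 49.5, so 50 by the normal approximation. The t-based calculation gives 51. One-sided 2.5% gives 63 (t-based 64). A margin of half of 0.64, that is 0.32 SD, gives 121 at one-sided 5%. So 0.50 SD with one-sided 5% is the reading that fits, although the plan does not state it.

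**Step 2: dilution with equal non-attendance.** Let mindfulness be worse by exactly 0.50 SD among attenders. The intention-to-treat difference is 0.50 × (1 − q). At q = 15% it is 0.425 SD, which is 0.075 SD inside the margin.

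Chance of declaring non-inferiority = Φ(0.50 × q / SE − 1.645), with SE = √(2/n).

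- n = 51: SE = 0.198; 0.075 / 0.198 = 0.379; Φ(−1.266) = 10.3%.
- n = 80: SE = 0.158; 0.075 / 0.158 = 0.474; Φ(−1.171) = 12.1%.

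| q in both arms | n = 51 | n = 80 |
|---|---|---|
| 0% | 5.0% | 5.0% |
| 5% | 6.4% | 6.9% |
| 10% | 8.2% | 9.2% |
| 15% | 10.3% | 12.1% |
| 30% | 18.7% | 24.3% |

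At one-sided 2.5%, with q = 15%, the chance is 5.7% (n = 51) or 6.9% (n = 80), against 2.5% without dilution.

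**Step 3: clustering.** The design effect 1 + (m − 1) × 0.07 is 1.63 for groups of 10 and 1.98 for groups of 15. With SE multiplied by its square root, and an analysis that accounts for it, the 10.3% becomes 8.9% to 8.4%, and the 12.1% becomes 10.2% to 9.6%.

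**Step 4: unequal non-attendance.** Let both programmes give 0.64 when attended and 0.14 when not, with non-attendance in Arm 1 only. The intention-to-treat difference is q × (0.64 − 0.14), which is 0.075 SD at 15% and 0.15 SD at 30%, against a true difference of zero among attenders. With 51 randomised per arm, the chance of declaring non-inferiority is 69% or 55%. In attenders only it is 78% or 74%. Here intention to treat pushes the arms apart.

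**The case against.** **The direction is not fixed.** A reader might infer that intention to treat always draws the arms together and so inflates false claims. The documents do not support that. It needs similar non-attendance and a true deficit among attenders, and Step 4 shows the opposite pattern. This objection stands, and it is also a reason to look at a second analysis set.

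**Whether the claim is false depends on the target.** If the question is the effect of offering the programme, a difference of 0.425 SD lies inside a 0.50 SD margin, and declaring non-inferiority is correct. The error is inflated only if the target is the effect in those who attend. The plan does not say which it means.

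**The plan has no non-inferiority test at all.** That gap is more basic than the choice of analysis set. It does not remove the point, because a test added under the present wording would be by intention to treat only.

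**The comparisons with Arm 3 give a partial check.** Study design plans Arm 1 vs Arm 3 and Arm 2 vs Arm 3. If poor attendance emptied both programmes, both would drift towards usual care. If psychoeducation also achieves 0.64, a deficit of 0.50 SD would put mindfulness level with Arm 3, which the Arm 1 vs Arm 3 comparison addresses directly. It would be wrong to say that nothing in the plan could reveal the problem, but this check is not sensitive to mild dilution.

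**The 15% is a drop-out rate.** The documents give no non-attendance rate. It would also be wrong to remove 15% from the sample (80 × 0.85 = 68) and then treat 15% of the remainder as non-attenders on the strength of the same figure. The figures above therefore use 51 and 80.

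**A per-protocol set loses the protection of randomisation.** This is true, and it is why that analysis should support intention to treat and not replace it. Requiring both to agree before non-inferiority is concluded is a debated trade-off with a power cost, and the material here does not justify imposing it.

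**Conclusion.** The point holds in limited form. The second hypothesis is sized as non-inferiority, only intention-to-treat analyses are planned, and neither a non-inferiority test nor an adherence-based supporting analysis is specified. Under the stated illustration, 15% non-attendance in both arms roughly doubles the chance of declaring non-inferiority when mindfulness is worse by the full margin among attenders: from 5% to about 10% with 51 per arm or 12% with 80, and to about 8% to 10% once clustering is allowed for. These figures rest on a margin, an alpha and a non-attendance rate that the plan does not state, and on taking the effect among attenders as the target. They show a possible size and do not predict what will happen in this trial.

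A reader might go further and conclude that intention to treat is the wrong main set, or that a non-inferiority finding from this trial would be unreliable. The documents support neither. This is a cheap improvement.

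**What to change.** In section 3, Data Analyses:

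- Keep intention to treat as the main analysis for all comparisons.
- State that Arm 1 vs Arm 2 is judged by the confidence limit for the difference against the margin, and give the outcome, the margin on that outcome's scale and the confidence level.
- Add a supporting per-protocol analysis of the same comparison. Fix the attendance threshold before results are seen, and record session attendance for every caregiver in Arms 1 and 2.
- Report the two analyses side by side, and discuss any disagreement when non-inferiority is interpreted.

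The cost is one further analysis and an attendance log. The documents do not mention attendance records, so the sponsor should confirm that they will be kept. The supporting set will be smaller and is defined by events after randomisation, so its estimate is open to selection and should be read with that in mind. Sample size, randomisation and the programmes are unchanged.
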